Official Title: Dietary Acid Load, Kidney Function and Disability in Elderly

NCT02691663

Date IRB-Approved: 6/27/2018

Study Title: Dietary acid load, kidney function and disability in elderly

Principal Investigator [name], **Co-investigator(s):** [name], [name], [name], [name]

Sponsor or funding source: (NIH/NIA and the Translational Science Center at Wake Forest University)

Background, Rationale and Context

Physical decline and frailty result from age- and disease-related impairments in organs and tissues. Frailty research has focused on the musculoskeletal, neurological and circulatory systems; yet interventions targeting these systems had limited success in preventing and treating functional decline. Given the aging of the US population, additional avenues for intervention development are urgently needed.

Fragility and disability in people ≥ 65 strongly correlate with declining kidney function and are evident even in early stages of chronic kidney disease (CKD)(1, 2). Moreover, CKD is highly prevalent in the elderly and associates with sarcopenia, osteopenia, and increased incidence of fractures/falls with hospitalization. Low serum bicarbonate and impaired acid-base homeostasis, also common in CKD, are increasingly appreciated as contributors to functional decline with advancing age(3-6). With aging, the adaptive response of the kidney to low serum bicarbonate and high metabolic acid load becomes maladaptive, facilitating CKD progression. Conversely, in adult patients with CKD, maintenance of serum bicarbonate at 24 meq/L with oral bicarbonate supplementation or increased consumption of base-forming foods slows CKD progression(7).

We proposed the current study and protocol based on the evidence summarized above and our preliminary studies, which suggest that: (1) In the Health Aging and Body Composition cohort (age 70-79) lower dietary acid load associates with stable kidney function over a 7-year follow-up, independent of age, race, gender, BMI, diabetes, hypertension or smoking status(8); (2) metabolomics analysis in participants of the African American Diabetes Heart Study suggested that it is feasible to segregate a urine metabolomics profile in the early stages of CKD (stages 2 and 3), and that lower consumption of base-forming fruits and vegetables and higher rates of acid excretion may be associated with CKD and its progression(9).

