The study will be conducted at the academic medical center, specifically the Clinical Research Unit (CRU) of the Wake Forest School of Medicine (WFSM) and with the support of the Pepper Center and Translational Science Institute. The participants will be recruited from the general community and evaluated and followed by the CRU.

Subjects selection criteria

Elderly at risk for disability with mild impairment of kidney function will be selected for this study.

Inclusion Criteria	Exclusion Criteria
Age 65+ years of age	Uncontrolled (>160 mg/dl fasting blood glucose), insulin-dependent diabetes and/or uncontrolled hypertension (SBP >160 , DBP >100)
SPPB (short physical performance battery) score >3	a current diagnosis of psychotic disorder or taking anti-psychotic medication
eGFR stage 2 (60-89) or 3 (30-59)	take more than 14 alcoholic drinks per week
	plan to relocate out of the study area within the 8 months
Net endogenous acid production (NEAP) >40 mEq/d	self-reported inability to walk across a room
Willing to provide informed consent and agrees to randomization	those who reside in nursing homes
Not involved in another intervention study	have difficulty communicating with study personnel due to speech or language or hearing problems
	had cancer requiring treatment in the past 1 year
	lung disease requiring regular use of corticosteroids at a dose of >7.5 mg/d for the last 3 months or use of supplemental oxygen
	cardiovascular disease (Class III or IV congestive heart failure)
	significant valvular disease, uncontrolled angina
	myocardial infarction, major heart surgery (i.e., valve replacement or bypass surgery) in past 6 months
	stroke, deep vein thrombosis, or pulmonary embolus in the past 6 months,
	Parkinson's disease or other progressive neurological disorder
	other medical or behavioral factors that in the judgment of the principal investigator may interfere with study participation or the ability to follow the intervention
	clinical judgment concerning safety or noncompliance
	Individuals with BMI <18.5 ; or unintentional weight loss $>4\%$ in last 6 months
	MoCA score under 24
	End Stage Renal Disease (ESRD) on dialysis or primary kidney disease
	Other illness of such severity that life expectancy is less than 12 months
	Any tobacco or nicotine product use in the past year
	Serum HCO ₃ >30 meq/L; serum K ⁺ out of normal range <3.5 or >5.2

Sample Size

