Oral bicarbonate supplementation group. Participants will be advised to continue their usual dietary and exercise pattern, but to take supplementation capsules. They will receive 0.3 meq/kg/day NaHCO₃, a dose based on the literature (14) and our Health ABC cohort preliminary study (8). The dose of 0.3 mg/kg/d NaHCO₃ was reported to reduce net acid excretion ~50% in individuals with similar daily acid load(14), and was effective in decreasing the rate of yearly eGFR decline in patients with hypertensive nephropathy; the dose has also been reported as safe (14, 15). NaHCO₃ will be provided in gelatin capsules containing 10 meq NaHCO₃, so that NaHCO₃ can be dosed to the nearest amount by total body weight; e.g, a 70kg person will receive 2 capsules daily, and an 85kg person would receive 3 capsules daily (14). Adherence will be assessed by pill count. Compliance will be measured at months 3 and 6 by determining the change from the baseline in net acid excreted (NEA) in 4hr-urine; an advantage of our approach is that compliance can be measured objectively rather than estimated. Oral bicarbonate has been used for decades in patients with CKD or distal renal tubular acidosis to treat metabolic acidosis(7), and is generally considered free from significant side effects. Participants will be withdrawn if any of the following occur: total carbon dioxide >30mmol/L, serum K+ <3.5mEq/L, hospitalization for congestive heart failure, weight gain >2kg due to edema, or increase in blood pressure (>15 mmHg systolic or diastolic) (7, 15).

Placebo group. Participants will be advised to continue their usual dietary and exercise pattern, but to take supplementation capsules (methylcellulose). To ensure participants' blinding, identical capsules will be taken and the total number of capsules kept constant. The placebo group will be followed in the same manner as the bicarbonate group; all assessors will be blinded with respect to group assignment.

Clinical assessments, laboratory analysis and analytical tests.

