Shortness of breath	4 (20)	1 (5)	1 (5)	3 (15)	2 (11)	0.97
Hospitalization	0	0	0	0	0	—

Data are expressed as number (%). Data are presented for all 20 participants at each time point except for the 1.0-mEq/kg per day dose, when 18 participants remained in the study.

- 4) **Increased risk of cardiovascular disease.** Lower all-cause mortality has been reported for individuals with serum bicarbonate >23 mmol/L vs. <23 mmol/L. A recent study however reported slightly higher risk of heart failure in kidney patients with serum bicarbonate >24 mmol/L. Serum bicarbonate >24 mmol/L did not however associate with any increase in mortality or ischemic events in the same group of patients (25). As an additional precaution, we will calculate bicarbonate deficit (if any) for each individual (=serum bicarbonate x 50% body weight (kg)) to help adjust dosing regimen and will monitor serum bicarbonate after the initiation of the intervention to adjust the amount of bicarbonate administered, if needed.
- 5) **Predisposition to vascular calcifications as a result of reduced solubility of calcium.** There is a theoretical concern from *in vitro* cell culture studies that raising extracellular pH may reduce solubility of calcium and predispose participants to vascular calcifications(26). There are currently no studies suggesting that this occurs *in vivo* with bicarbonate therapy, but this issue has not yet been addressed specifically in clinical trials. This may be more relevant to patients with advanced kidney disease and patients with Ca x Pi ratio >50, receiving phosphate binders, who are in fact prone to vascular calcification, than to population that we plan to recruit (CKD2 and 3a)(27).

- 6) Simultaneous ingestion of bicarbonate and non-absorbable antacids (aluminum and magnesium carbonate in combination with cation-exchange resins). This causes formation of easily absorbable bicarbonate in the small intestine and in this case metabolic alkalosis can occur, if bicarbonate excretion by the kidney is limited, again unlikely in participants with CKD 2 and 3a. Nevertheless, participants will be advised to avoid concomitant use of non-absorbable antacids and bicarbonate.
- 7) DXA scans. Exposure to radiation from the hip DXA (20 mRem total) for baseline and follow-up scans.

Adequacy of protection against risks

Recruitment and Informed Consent

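### The bicarbonate deficit formula has no target term, so it is never zero and rises with serum bicarbonate; separately, two sections give different weight bases and rounding for the dose

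*Combined protocol and SAP*

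**What the plan says.** **Deficit formula.** Potential Risks, item 4 (cardiovascular disease), says the team will "calculate bicarbonate deficit (if any) for each individual (=serum bicarbonate x 50% body weight (kg)) to help adjust dosing regimen", and in the same sentence that it "will monitor serum bicarbonate after the initiation of the intervention to adjust the amount of bicarbonate administered, if needed". The lead-in to this is mixed. It cites lower mortality for "serum bicarbonate >23 mmol/L vs. <23 mmol/L", then a "slightly higher risk of heart failure in kidney patients with serum bicarbonate >24 mmol/L", then no excess of deaths or ischaemic events above 24 in the same patients. No target for this trial is stated. The nearest figure is in Background, Rationale and Context, which describes "maintenance of serum bicarbonate at 24 meq/L with oral bicarbonate supplementation" in adults with CKD as slowing progression.

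**Dosing rule.** Under Interventions and Interactions, the paragraph on the oral bicarbonate group sets 0.3 mEq/kg/day. It names capsules of 10 mEq and says the product "can be dosed to the nearest amount by total body weight". A 70 kg person gets two capsules, and "an 85kg person would receive 3 capsules daily".

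The section on safety measures during the intervention period uses lean body weight instead, rounded to half a capsule, with half-dose capsules made by the pharmacy as needed. It gives about 25 mEq/day for an 85 kg patient, in three daily doses, and two doses a day at 70 kg.

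**The concern.** A deficit is a shortfall from a reference level. The printed expression has no reference level, so it describes how much bicarbonate is present in an assumed space of half the body weight, not how much is missing. It allows in words that some participants have no deficit, but it can never return zero. It also gives its largest value to the participant with the highest serum bicarbonate, which is the wrong direction for a precaution about high bicarbonate. Anyone using it literally to help adjust a dose could not tell who needs more and who needs none.

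The second matter concerns the operative dose. Total and lean body weight are different quantities, and rounding to whole or half capsules can give different doses for the same person. Whoever dispenses has two rules and no statement of which governs.

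**Working it through.** **1. The plan's own dose figures.** Inputs: 0.3 mEq/kg/day and 10 mEq per capsule (oral bicarbonate group paragraph); weights of 70 and 85 kg (both sections).

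- 85 kg: 0.3 × 85 = 25.5 mEq/day, which reproduces the stated figure of about 25.
- 70 kg: 0.3 × 70 = 21 mEq/day = 2.1 capsules, so two capsules (20 mEq) under whole- or half-capsule rounding.
- 85 kg in capsules: 25.5 / 10 = 2.55. The nearest whole capsule is 3 (30 mEq); the nearest half capsule is 2.5 (25 mEq).

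The two sections therefore agree at 70 kg. At 85 kg they differ by 30 − 25 = 5 mEq/day if the three capsules are all 10 mEq.

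**2. Which weight basis fits the 25 mEq figure?** On total weight, 25 / 85 = 0.294 mEq/kg, close to 0.3. With half-capsule rounding, 25 mEq corresponds to calculated doses from 22.5 to 27.5 mEq, so the dosing weight must be at least 22.5 / 0.3 = 75 kg. If that were lean weight, an 85 kg patient would need to be at least 75 / 85 = 88% lean. The documents give no lean fraction. As an assumption for illustration, 65–80% lean gives 0.3 × 85 × 0.65 = 16.6 to 0.3 × 85 × 0.80 = 20.4 mEq/day, or 1.5 to 2 capsules, below the stated 25. The only scheduled DXA is of the hip, and no assessment is described as supplying whole-body lean weight for dosing.

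**3. The deficit formula.** Inputs: the printed expression (Potential Risks, item 4); 30 mEq/L as the highest serum bicarbonate allowed at entry (Subjects selection criteria); 24 mEq/L from the Background and 23 mmol/L from item 4 as illustrative targets only.

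Printed: HCO3 × 0.5 × weight. With a target: (target − HCO3) × 0.5 × weight, set to zero if negative.

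| HCO3, 70 kg person | Printed | Target 24 (assumed) | Target 23 (assumed) |
|---|---|---|---|
| 20 | 20 × 35 = 700 mEq | 4 × 35 = 140 mEq | 3 × 35 = 105 mEq |
| 24 | 24 × 35 = 840 mEq | 0 | 0 |
| 30 | 30 × 35 = 1,050 mEq | 0 | 0 |

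At 70 kg the printed value rises by 35 mEq for each 1 mEq/L of serum bicarbonate. The version with a target falls by the same amount until it reaches zero.

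**The case against.** The strongest reply is that the formula does not set the dose. The assigned dose is 0.3 mEq/kg/day. The formula sits in a risk narrative and only helps with adjustment, and the same sentence provides for monitoring serum bicarbonate, which needs no formula. A clinician would probably supply the missing target. This stands as a limit on harm. It does not make the printed expression usable. In the schedule, the first serum bicarbonate or total CO2 after randomization is in the 3-month metabolic panel, so before then a calculation from entry values is the only stated route to individual adjustment.

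A delta sign could have been lost in conversion to text. Symbols are lost elsewhere: a box follows the 0.05 in the Sample Size section. No such box appears in this sentence, so a loss here is speculation, and a delta would still leave the target unstated.

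On the weight basis, the 70 kg example in the safety section could grammatically mean 70 kg of lean weight, lean body mass is a planned data item, and both sections cite the same outside study for dosing. These points stand, so total weight is the better-supported reading and not a certainty.

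A reader might infer that participants with high bicarbonate would be given more, or given hundreds of mEq. The documents do not support that, because nothing says how the calculated deficit becomes a dose. A reader might also reconcile the two sections by taking the three capsules at 85 kg as two full and one half-dose capsule, which gives 25 mEq. The paragraph with that example names only 10 mEq capsules, so its plain reading is 30 mEq, and the documents do not say what was intended.

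**Conclusion.** Both parts hold, at minor severity.

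1. The deficit formula is wrong as written: always positive, and largest where there is no deficit. That follows from the expression alone. Only the corrected values rest on an assumed target. The consequence for any participant's dose cannot be sized. Harm is limited by the weight-based dose, exclusion above 30 mEq/L at entry, monitoring, withdrawal above 30 mmol/L total CO2 and twice-yearly board review.
2. The dosing rule is stated on two weight bases with different rounding. At 85 kg the gap is 5 mEq/day on the plain reading of the capsule example. The size of the lean-versus-total difference depends on a lean fraction that the documents do not give.

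It would be going too far to infer bias in the net acid excretion comparison or a loss of power. The documents do not show which rule was applied to whom, and neither the sample size nor the analysis model uses the formula or the weight basis.

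**What to change.** In Potential Risks, item 4, delete the deficit formula. Alternatively, replace it with (target − measured serum bicarbonate) × 0.5 × body weight, set to zero at or above the target. The sponsor should state the target (24 mEq/L is only an illustration) and say how the result changes the dose.

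In the oral bicarbonate group paragraph and the intervention-period safety section, state the same weight basis and the same rounding. The rule that best fits the protocol's figures is 0.3 mEq/kg/day of total body weight to the nearest half capsule: 20 mEq/day at 70 kg and 25 mEq/day at 85 kg. If that rule is adopted, bring the three-capsule example into line by giving the dose in mEq and the strength of each capsule. If lean weight was intended, say how it is obtained.

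The cost is a few sentences in three places and a check of the pharmacy instructions. Visits, sample size and analysis do not change. Parts of the analytical text are in the past tense; if dosing is already complete, report which rule was used.

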prot=g of protein consumed per day and pot=meqs of potassium consumed per day(19). The Short Physical Performance Battery (SPPB) is a well-characterized global measure of lower-extremity function and mobility. It will be assessed during screening (20, 21), at 3 and 6 months. The test consists of gait speed, chair stands, and balance; it is a strong predictor of disability and mortality in initially non-disabled older persons. SPPB scores of 4-9 have already been successfully used as a range associated with risk for developing mobility disability(21). The 400-meter walk is a measure of aerobic endurance where participants are instructed to complete the 400m distance (on a flat indoor surface) at their normal pace and the time to complete the walk is recorded in minutes and seconds. A comprehensive metabolic profile (CMP), including tCO₂, electrolytes, blood glucose and creatinine will be assessed at baseline and at 6-month follow-up. In conjunction with data from urine collections and analysis, CMP will allow calculation of fractional excretion of Na⁺, K⁺, Cl⁻, and the anion gap(22).

Bone Health. Because the kidney's capacity to excrete acid declines with age, acid-producing diets lead to a positive balance of protons and mild (often) subclinical acidosis. This acidic milieu facilitates release of Ca²⁺ from bone and increases bone turnover; it impairs osteoblast function and activates osteoclasts through stimulation of the proton-sensing receptor OGR1 and release of prostaglandin E2. Phosphate and bicarbonate released from bone mineral neutralize acid by a physicochemical reaction, leading to further Ca²⁺ release from the bone. In addition, renal Ca²⁺ excretion increases, through suppression of Ca²⁺ transporters and the calcium-sensing receptor (CaSR), which is exquisitely pH sensitive. CaSR regulates both renal Ca²⁺ absorption and parathyroid hormone release. Since a dietary acid load does not alter intestinal Ca²⁺ absorption, negative Ca²⁺ balance persists as long as the proton balance remains positive (33-73). This pathophysiologic mechanism explains why it is of great interest that we evaluate bone density in our study, which is testing the feasibility of neutralizing diet-dependent acid load in the elderly.

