collection of these data throughout the study. The first recall will be conducted at the SV to review all procedures and tools to be used. A “Food Amounts” booklet containing 2-D visual portions will be provided to the participant for use in standardizing portion sizes. Subsequent recalls will be conducted by telephone with trained interviewers from the CRU placing unscheduled telephone calls to participants at seven additional timepoints. When contacted by the staff, subjects will be asked to recall and report their dietary intake from the previous day’s 24-hour period. In addition to the first in-person SV recall, telephone recalls will be done within one week of the SV (1) to further assess eligibility (an average of both protein intake and K+ will be used to calculate the NEAP score), and within a 1-week period of each follow-up visit for a total of eight recalls during the study. Recalls will be randomly scheduled and will reflect both weekday and weekend intakes.

At the baseline visit and remaining in-clinic follow up visits, participants will spend approximately 4hr in the Clinical Research Unit (CRU), have their physical ability tested (FV2 and FV3 only), have blood drawn for blood gas analysis as well as blood for cystatin c and blood for storage. The blood gas draw will be performed in the CRU. Urine will be collected over the 4hr period (this is necessary because urine collections need to be monitored and refrigerated). Participants will be encouraged to take 500 ml of water during their stay at the CRU, to stimulate urine production. During these visits (not at FV2) the participants will also provide information about their dietary habits using the VioFFQ™ (Viocare, Inc., Princeton, NJ), which is a validated, web-format system for collecting food frequency data on a subject’s dietary behavior and food use patterns. The questionnaire will be self-administered. Participants will also receive a DXA scan of their hip at BV and FV3.

Table showing Study Schedule of events	SV	BV	FV1	FV2	FV3
Location of Visit	CRU	CRU	Phone Call	CRU	CRU
Study Week Number Activity/Assessment	-1 wk	0	1 mo	3 mo	6 mo
Informed Consent	X				
Cognitive Screen (MoCA)	X				
Fasting blood draw (CMP)	X			X	X
Urinalysis (Spot Urine)	X				X
SPPB	X			X	X
400m walk test		X		X	X
VITALS	X	X		X	X
DXA		X			X
24-hour Diet Recall to calculate NEAP	X		X	X	X
Medical History and Medications	X		X	X	X
Food Frequency		X			X
Blood Gas, Cystatin C, blood for storage		X			X

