4hr urine collection to determine (Net acid excretion (NAE); urinary nitrogen and Ca ⁺² excretion, uACR) Urea Nitrogen, Uric Acid, Urine Creatinine,) and obtain urine for storage		X		X	X
Randomization		X			
Urine Metabolomics		X			X
Dispense Medication		X		X	
Medication Adherence				X	X

Outcome Measure(s)

1. Determine the feasibility of achieving ~50% reduction in net acid excretion (NEA/Cr meq/g) following 6 months of oral bicarbonate supplementation, compared to the placebo group
2. Determine
 - a. Recruitment yields
 - b. Adherence to the assessment schedule
 - c. Compliance with intervention over 6 months

- d. Collect data on variability and longitudinal correlation structure of kidney function, lean body mass and functional outcomes
- 3. Ascertain feasibility of using metabolomics to detect changes in kidney function following the intervention

Analytical Plan

All data will be entered as collected into web-based forms; analysis datasets will be stored in SAS. All data will be examined monthly by histograms and scatterplots to check for internal inconsistencies, unusual data needing further verification, and outliers. In few case of outliers and unusual data, participant's charts were reviewed to ascertain whether any adverse measurement conditions or circumstances or potential artefacts existed. Only in cases where measurement artefacts were identified or other circumstances were found that adversely affected data collection were the measurements removed. Otherwise all data remained within the data set. Sensitivity analyses will be performed with and without potential outliers included in individual analyses.

For each analysis, regression diagnostics and exploratory analyses will be performed to find appropriate transformations of the variables, if needed. Priority in choosing a transformation will be to satisfy: 1) linearity, 2) homogeneity, and 3) normality assumptions. Initial analyses will follow the "intent-to-treat" principle. Due to having low power to detect potentially important relationships within this pilot, emphasis will be on using confidence intervals to described estimated parameters and relationships. When hypothesis testing is performed, we will set the significance level at $\alpha=0.05$. We have chosen this level for all hypothesis tests within the pilot because risk of missing an association by making a Type II error outweighs the concern for falsely identifying relationships via a Type I error.

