Power analysis: Based on published studies, we have assumed a 6-month change in NAE/Cr of 16.5 mEq/g within groups. Assuming a conservative 12.5% loss-to-follow-up at 6 months (35 participants/group remaining), we will have 80% power to detect a difference between groups in NAE/Cr as small as 11.4 mEq/g with a two-sided Type I error rate of 0.05. Considering that expected change in NEA/Cr will be about 20-30 meq/d we should be able to detect clinically important changes in NEA/Cr from the proposed intervention. For correlational analyses, 80 participants will allow us to detect correlation coefficients of 0.31 or larger with at least 80% power assuming a 2-sided 0.05 □.

Other Exploratory/Sensitivity Analyses:

Do NEAP and NAE correlate at baseline, when controlled for kidney function and caloric intake?

Do NAE and calcium excretion correlate at baseline and other time points, when controlled for kidney function and calcium intake?

Do NAE and sodium intake correlate? Do NAE and sodium excretion in the urine correlate? (An important one, if so, we will need to treat sodium intake as a confounder. There is physiological feasibility that these two may correlate.)

Does NEAP calculated from food recalls correlate with NEAP calculated from FFQs?

Human Subjects Protection

Human Subjects Involvement and Characteristics

We plan to recruit and randomize up to 83 older men and women who meet the inclusion/exclusion criteria described above. Participants will be randomized to bicarbonate capsules or placebo for 6 months. All assessments will be conducted during following visits and phone calls: screening phone call, 1 screening visit (SV1); 1 baseline visit (BV1); 1-month phone call, 3-months mid-intervention follow-up visit (FV1); and 1 post-intervention follow-up visit at 6-month (FV2).

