There is plethora of published data on use of bicarbonate supplementation and that has simplified determination of a safe dose for this study. An average dose per 85 kg patient will be ~ 25 meq/d as gel capsules containing 10 meq NaHCO₃ with sucrose in 3 daily doses; placebo capsules will contain sucrose only. Per published studies(14), each subject will be dosed to the nearest "one-half capsule" by lean body weight in kg (e.g., a 70 kg subject will receive two doses daily; capsules with half a dose can easily be prepared by our pharmacy as needed)). Participants will be monitored for evaluation of medication tolerability. Adherence to study medication will be assessed by pill count and deducted from net acid excretion measurements. Participants will be withdrawn from the study at their FV2 visit if their total carbon dioxide >30 mmol/L, their eGFR falls below 15 ml/min, they experience weight gain of more than 2 kg due to edema, develop serum potassium<3.5mmol/L, or have an increase in blood pressure (systolic or diastolic) of more than 15 mmHg (7, 15). These parameters will be assessed at each visit.

Safety measures during the assessments

All study assessments will be conducted by trained and certified staff. Safety precautions will be taken during all testing (e.g. gait speed) by applying standardized stopping criteria. If the participant reports pain, tightness or pressure in the chest, feeling faint, lightheaded or dizzy, or significant other medical problems, the test will be stopped. The PI and Co-I [name], will review lab data for medical concerns. When there are medically relevant findings, the participant will be told the cause for concern, and may be advised to consult his or her physician. If given permission by the participant, a letter will be sent to her/his primary care physician stating the concern.

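### Under the schedule's visit labels, the FV2 safety rule takes people out of the study rather than off the capsules, so their 6-month NAE/Cr is lost; the FV2 label and the stopping criteria also need aligning

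*Combined protocol and SAP*

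**What the plan says.** **The rule.** Under *Safety measures during the bicarbonate intervention period*: "Participants will be withdrawn from the study at their FV2 visit if their total carbon dioxide >30 mmol/L", or if one of the other criteria is met. These include "their eGFR falls below 15 ml/min". The paragraph ends: "These parameters will be assessed at each visit".

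**A second version.** The description of the bicarbonate group under *Interventions and Interactions* says "Participants will be withdrawn if any of the following occur". It names no visit and does not say that people leave the study. It lists heart-failure hospitalization, which the safety section omits, and has no eGFR criterion.

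**When FV2 is.** The schedule table has FV1 as a 1-month phone call, FV2 at month 3 and FV3 at month 6. The visit narrative agrees: participants "have their physical ability tested (FV2 and FV3 only"). The "Dispense Medication" row is marked at baseline and FV2, so the second capsule supply goes out at month 3. *Human Subjects Involvement and Characteristics* labels the visits differently: "3-months mid-intervention follow-up visit (FV1); and 1 post-intervention follow-up visit at 6-month (FV2").

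**When safety bloods are drawn.** The table places the comprehensive metabolic panel (CMP) at screening, month 3 and month 6. The assessments text says "electrolytes, blood glucose and creatinine will be assessed at baseline and at 6-month follow-up", with no month-3 draw.

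**What the analysis promises.** The *Analytical Plan* states that initial analyses are intent-to-treat. Aim 1 uses a mixed-effects ANCOVA with a 6-month contrast. The plan says this can be unbiased when missingness relates to outcomes at other times.

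**Other responses to the same signals.** *Potential Risks*, item 2, pauses capsules during an intercurrent illness with hypokalemia. Item 4 adjusts the dose on serum bicarbonate.

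**The concern.** No section keeps a withdrawn participant in follow-up. On the schedule's labels, someone who meets a criterion at month 3 gives a month-3 urine and then leaves. The month-6 NAE/Cr is lost. So are the measures that the table collects after baseline only at FV3: DXA, cystatin C, blood gas and urine metabolomics. (The visit narrative can be read as adding blood gas and cystatin C at month 3.) Aim 2 exists partly to collect longitudinal data of this kind.

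These participants are the ones in whom the intervention could not be sustained. Their off-capsule month-6 values belong in an intent-to-treat contrast, and a likelihood model cannot recover them from a month-3 value taken on capsules. Aim 2 would count them within loss to follow-up and missing measurements, but does not ask for rule-based stops to be shown separately.

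Staff also need one rule at month 3. As written, the visit label, the criteria, the CMP timing and the required action (withdraw, pause or adjust the dose) differ between sections.

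**Working it through.** **Inputs**
- 16.5 mEq/g, 35 per group after 12.5% loss, detectable difference 11.4 mEq/g, 80% power, two-sided 0.05 (*Sample Size*, repeated in *Power analysis*). The plan words 16.5 as a change; it functions as a standard deviation.
- Expected effect *E* = 20 to 30 (same places). The plan gives meq/d; it is read here as mEq/g and as the average effect in those still in the study.
- Share *w* of the bicarbonate arm stopped at month 3: not in the documents. Assumed 2%, 5% or 10%, about 1, 2 or 4 of 41 (83/2 = 41.5).
- Fraction *r* of the effect lost by month 6 after stopping: assumed 1 (full return to placebo level) or 0.5.

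**1. The plan's own figure.** Standard error = 16.5 × √(2/35) = 3.94. Two-sample t power at 11.4 is 81.3%, against 80% stated. It reproduces with 16.5 as the SD.

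**2. What the contrast estimates**
- With everyone's month-6 value: (1 − w)E + w(1 − r)E = E(1 − wr).
- With stopped participants' month-6 values missing, the model projects from those still in the study and gives about E.
- Overstatement ≈ w × r × E.

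| Assumed share | E = 20, r = 1 | E = 20, r = 0.5 | E = 30, r = 1 |
|---|---|---|---|
| 2% | 0.4 | 0.2 | 0.6 |
| 5% | 1.0 | 0.5 | 1.5 |
| 10% | 2.0 | 1.0 | 3.0 |

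The gap scales with the share: 20% at E = 20 and full return would give 4.0. Against the percentage target, a 50% on-capsule reduction corresponds to 50 × (1 − w) = 49%, 47.5% or 45% across everyone randomised.

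**3. Does the retained month-3 value repair this?** A simulation used 400,000 per arm, SD of change 16.5, assumed correlation 0.5, E = 20 and full return.
- All month-6 data kept: 19.6, 19.0 and 18.0 at 2%, 5% and 10%.
- Month 6 missing, month 3 kept: 20.0 each time.
- The gap was the same whether stops were random or favoured a larger month-3 fall, and whether they occurred in one arm or both.
- If stopped participants had 0.5 or 1.5 times the average effect, the gap ran from 0.33 to 0.45, 0.85 to 1.15 and 1.74 to 2.26.

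So month 3 carries some information about the individual, but not the shift caused by stopping.

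**4. Size against precision**
- At E = 20 and full return, 0.4, 1.0 and 2.0 are 0.10, 0.25 and 0.51 of the unadjusted standard error of 3.94.
- At correlation 0.5 the baseline-adjusted standard error at 35 per arm is 3.94 × √(1 − 0.25) ≈ 3.4, giving about 0.12, 0.29 and 0.59.
- Power is 0.999 at 20 mEq/g and 0.994 at 18 with 35 per arm, and 0.988 at 18 with 31 per arm.

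**5. Is a share of a few percent plausible?** The blood-pressure criterion alone (a rise above 15 mmHg) can be met by chance. With no true change and an assumed SD of systolic change of 8, 10 or 12 mmHg, 1 − Φ(15/SD) = 3%, 7% or 11%, in either arm.

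**6. The two label schemes**

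| | Schedule table | Human-subjects section |
|---|---|---|
| FV2 | Month 3 | Month 6 |
| Month-6 NAE/Cr after a trigger at FV2 | Not collected | Can be collected |
| When the FV2 rule acts | Mid-dosing | End of dosing |

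A check of every criterion at every visit does not fit the schedule either: FV1 is a phone call and the baseline visit has no CMP.

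**The case against.** **The loss is conditional.** It follows only from the schedule's labels. This stands. The schedule is the fuller source and the re-dispensing at FV2 fits it, but the one certain defect is the contradictory label.

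**The size rests on assumption.** With full return the gap is simply share times effect, so the simulation adds no evidence about the share. *Potential Risks* judges alkalosis unlikely and cites a pilot in which the proposed dose range showed no difference in adverse effects from placebo. This stands; the figures are a range, not a forecast.

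**An on-capsule estimate is defensible.** Aim 1 asks whether about a 50% reduction is achievable with supplementation, in an exploratory study that emphasises confidence intervals. That is fair as a choice of estimand, but it is not the one the plan states.

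**Intent-to-treat is not abandoned.** A reader might infer that withdrawn participants drop out of the analysis. The documents do not support that: the month-3 value stays in the model, nothing moves anyone out of the randomised arm, and the plan states its missing-data claim as a condition. A reader might also infer that month 3 says nothing about month 6, which is too strong when a correlation of 0.5 is assumed.

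**Part is handled elsewhere.** Withdrawals would appear in Aim 2's loss to follow-up, and a monitoring board meets twice a year. Neither gives the rate of rule-based stops by arm, nor settles which visit the rule applies to.

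**Conclusion.** The point holds, with modest weight. On the schedule's labels, participants who trigger the rule lose their month-6 NAE/Cr and the FV3-only measures, and the Aim 1 contrast shifts from the stated intent-to-treat effect toward an on-capsule one. The overstatement is about 0.4 to 2.0 mEq/g at an effect of 20, for assumed stop shares of 2% to 10% and full loss of effect after stopping. It is half that with half return, and zero if FV2 is month 6.

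A reader might infer that the trial is underpowered or that the Aim 1 conclusion is unsafe. Neither follows: power at 18 mEq/g is still 0.994, and a shift of this size is unlikely to change whether a reduction near 50% looks achievable. Nor do the documents show that month-3 safety bloods are absent; the schedule includes them and one sentence leaves them out.

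The plan should still be corrected, because the label conflict leaves the rule unclear under either reading and the remedy is cheap. Confidence is medium: the trigger rate and the intended FV2 label are not settled in the documents.

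**What to change.** 1. Use the schedule table's visit labels and CMP timing throughout, correcting the assessments text and the human-subjects section. Replace the statement about checks at every visit with the visits at which each criterion can be measured.
2. Merge the two criteria lists into one, applied whenever a criterion is met. State how it fits with the pause for intercurrent illness and the dose adjustment on serum bicarbonate in *Potential Risks*. Clinical thresholds are for the sponsor.
3. Replace withdrawal from the study with stopping study capsules. Keep the scheduled month-6 visit, including the 4-hour urine, for those who agree, and analyse those data in the randomised arm.
4. In Aim 2, report rule-based capsule stops by arm, separately from loss to follow-up.

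**Cost.** Amendment wording, and month-6 visits already planned for perhaps 1 to 4 bicarbonate participants under the assumed shares, plus any placebo participants who meet a criterion. Off-capsule values will dilute the estimated effect slightly (0.4 to 2.0 of 20 mEq/g at full return), which is what intent-to-treat intends.
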